# 5. INVESTIGATIONAL MEDICINAL PRODUCTS (IMP)

# 5.1. Randomization, Blinding and Treatment Codes

Subjects will be assigned a screening number at the time of consent. Randomization and Day 1 visits cannot occur until subject eligibility has been confirmed.

Once eligibility has been confirmed and prior to or during the Day 1 visit, the Investigator or designee will randomize the subject using the Interactive Web Response System (IWRS). Once a subject number has been assigned to a subject, it will not be reassigned to any other subject. The subject number assignment and randomization may be performed up to 3 days prior to the in-clinic Day 1 visit provided that all screening procedures have been completed and subject eligibility has been confirmed.

Subjects will be randomized in a 1:1 ratio to Treatment Group 1 or Treatment Group 2.

Randomization will be stratified by NRTI use (F/TAF vs. F/TDF) and documented or suspected history of NRTI resistance. The following NRTI-associated mutations will be considered as having NRTI resistance: M41L, K65R/E/N, D67N, T69 insertions, K70R, L74I/V, Y115F, Q151M, M184I/V, L210W, T215F/Y, K219Q/E/R/N, T69D, K70E/G/M/Q/S/T, V75A/S/M/T. NRTI resistance will be stratified by the following categories:

- 1. K65R/E/N, or 3 or more thymidine analogue mutations (TAMs) that include M41L or L210W, or T69 insertions, (TAMs are: M41L, D67N, K70R, L210W, T215F/Y, and K219Q/E/R/N)
- 2. Any other pattern of NRTI resistance of M41L, D67N, K70R, L74I/V, Y115F, Q151M, M184I/V, L210W, T215F/Y, K219Q/E/R/N, T69D, K70E/G/M/Q/S/T, V75A/S/M/T.
- 3. None of these mutations/No NRTI resistance

For subjects that qualify for more than one resistance category, stratification will be prioritized by category 1, then 2, then 3 above. The IWRS will assign study drug bottle numbers of blinded B/F/TAF FDC + placebo to match DTG + placebo to match F/TAF FDC, **or** DTG+F/TAF FDC + placebo to match B/F/TAF FDC, at each study visit for each subject.

## **5.1.1.** Procedures for Breaking Treatment Codes

In the event of a medical emergency where breaking the blind is required to provide medical care to the subject or in the case of pregnancy that occurs while on study drug, the investigator may obtain treatment assignment for that subject. Gilead recommends but does not require that the investigator contact the Gilead medical monitor before breaking the blind. Treatment assignment should remain blinded unless that knowledge is necessary to determine subject emergency medical care or in the event of a pregnancy that occurs while on study drug. The rationale for unblinding must be clearly explained in source documentation and on the electronic case report form (eCRF), along with the date on which the treatment assignment was obtained. The investigator is requested to contact the Gilead medical monitor promptly in case of any treatment unblinding.

Blinding of study treatment is critical to the integrity of this clinical trial and therefore, if a subject's treatment assignment is disclosed to the investigator, the subject will have study treatment discontinued. All subjects will be followed until study completion unless consent to do so is specifically withdrawn by the subject.

Gilead Pharmacovigilance and Epidemiology (PVE) (formerly referred to as Drug Safety and Public Health may independently unblind cases for expedited reporting of suspected unexpected serious adverse reactions (SUSARs).

# 5.2. Description and Handling

#### **5.2.1.** Formulation

### 5.2.1.1. B/F/TAF (50/200/25 mg) and PTM Tablets

The B/F/TAF (50/200/25 mg) tablets are capsule-shaped, film-coated purplish-brown, debossed with "GSI" on one side of the tablet and "9883" on the other side of the tablet. Each tablet core contains 50 mg of bictegravir, 200 mg of emtricitabine, and 25 mg of tenofovir alafenamide. In addition to the active ingredients, the B/F/TAF tablets contain croscarmellose sodium, magnesium stearate, and microcrystalline cellulose. The tablet cores are film-coated with iron oxide red, iron oxide black, polyethylene glycol, polyvinyl alcohol, talc, and titanium dioxide.

The PTM B/F/TAF tablets are capsule-shaped, film-coated purplish-brown, debossed with "GSI" on one side of the tablet and "9883" on the other side and are identical in physical appearance to B/F/TAF tablets. The placebo tablets contain microcrystalline cellulose, lactose monohydrate, croscarmellose sodium and magnesium stearate. The tablet cores are film-coated with iron oxide red, iron oxide black, polyethylene glycol, polyvinyl alcohol, talc, and titanium dioxide.

## 5.2.1.2. DTG (50 mg) and PTM Tablets

Dolutegravir 50-mg tablets are round, film-coated yellow, debossed with "50" on one side and debossed with "SV 572" on the other side. Each tablet core contains 50 mg of dolutegravir. In addition to the active ingredient, DTG tablets contain D-mannitol, microcrystalline cellulose, povidone K29/32, sodium starch glycolate and sodium stearyl fumarate. The tablet cores are film-coated with iron oxide yellow, polyethylene glycol, polyvinyl alcohol, talc and titanium dioxide.

The PTM DTG tablets are round, film coated yellow, debossed with "50" on one side and debossed with "SV 572" on the other side. PTM DTG tablets are identical in physical appearance to DTG 50-mg tablets. The placebo tablet cores contain microcrystalline cellulose, lactose monohydrate, croscarmellose sodium and magnesium stearate. The tablet cores are film-coated with iron oxide yellow, polyethylene glycol, polyvinyl alcohol, talc and titanium dioxide.

# 5.2.1.3. F/TAF (200/25 mg) and PTM Tablets

The F/TAF (200/25 mg) tablets are rectangular-shaped, film-coated blue, debossed with "GSI" on one side of the tablet and "225" on the other side of the tablet. Each tablet core contains 200 mg of emtricitabine and 25 mg of tenofovir alafenamide. In addition to the active ingredients, the F/TAF tablets contain croscarmellose sodium, magnesium stearate and microcrystalline cellulose. The tablet cores are film-coated with FD&C blue #2/indigo carmine aluminum lake, polyethylene glycol, polyvinyl alcohol, talc and titanium dioxide.

The PTM F/TAF tablets are rectangular-shaped, film-coated blue, debossed with "GSI" on one side of the tablet and "225" on the other side of the tablet. PTM F/TAF tablets are identical in physical appearance to F/TAF (200/25 mg) tablets. The placebo tablet cores contain microcrystalline cellulose, lactose monohydrate, croscarmellose sodium and magnesium stearate. The tablet cores are film-coated with FD&C blue #2/indigo carmine aluminum lake, polyethylene glycol, polyvinyl alcohol, talc and titanium dioxide.

# 5.2.2. Packaging and Labeling

# 5.2.2.1. B/F/TAF (50/200/25 mg) and PTM Tablets

B/F/TAF tablets and PTM B/F/TAF tablets are packaged in white, high density polyethylene (HDPE) bottles. Each bottle contains 30 tablets, silica gel desiccant and polyester packing material. Each bottle is enclosed with a white, continuous thread, child-resistant polypropylene screw cap with an induction-sealed and aluminum-faced liner.

Study drug(s) to be distributed to centers in the US and other participating countries shall be labeled to meet applicable requirements of the US FDA, EU Guideline to Good Manufacturing Practice - Annex 13 (Investigational Medicinal Products), and/or other local regulations.

# 5.2.2.2. DTG (50 mg) and PTM Tablets

DTG 50-mg tablets and PTM tablets are packaged in white, HDPE bottles. Each bottle contains 30 tablets. Each bottle is enclosed with a white, continuous thread, child-resistant polypropylene screw cap with an induction-sealed and aluminum-faced liner.

Study drug(s) to be distributed to centers in the US and other participating countries shall be labeled to meet applicable requirements of the US FDA, EU Guideline to Good Manufacturing Practice - Annex 13 (Investigational Medicinal Products), and/or other local regulations.

#### 5.2.2.3. F/TAF (200/25 mg) and PTM Tablets

F/TAF (200/25 mg) and PTM tablets are packaged in white, HDPE bottles. Each bottle contains 30 tablets, silica gel desiccant, and polyester packing material. Each bottle is enclosed with a white, continuous thread, child-resistant polypropylene screw cap with an induction-sealed and aluminum-faced liner.

Study drug(s) to be distributed to centers in the US and other participating countries shall be labeled to meet applicable requirements of the US FDA, EU Guideline to Good Manufacturing Practice - Annex 13 (Investigational Medicinal Products), and/or other local regulations.

# 5.2.3. Storage and Handling

Study drugs should be stored at controlled room temperature of 25°C (77°F); excursions are permitted between 15°C and 30°C (59°F and 86°F). Storage conditions are specified on the label. Until dispensed to the subjects, all bottles of study drugs should be stored in a securely locked area, accessible only to authorized site personnel.

To ensure the stability and proper identification, study drug(s) should not be stored in a container other than the container in which they were supplied. Keep the bottle tightly closed to protect from moisture.

Consideration should be given to handling, preparation, and disposal through measures that minimize drug contact with the body. Appropriate precautions should be followed to avoid direct eye contact or exposure through inhalation when handling.

# 5.3. Dosage and Administration of B/F/TAF and DTG+F/TAF

Study drug B/F/TAF FDC, DTG, F/TAF FDC, and PTM tablets will be provided by Gilead.

**Treatment Group 1:** FDC B/F/TAF (50/200/25 mg) + PTM of DTG (50 mg) + PTM FDC of F/TAF (200/25 mg) administered orally, once daily, without regard to food (total of 3 tablets)

**Treatment Group 2:** DTG (50 mg) + FDC of F/TAF (200/25 mg) + PTM FDC B/F/TAF (50/200/25 mg) administered orally, once daily, without regard to food (total of 3 tablets)

After the End of Blinded Treatment Visit, all subjects who choose to participate in the open label extension will receive B/F/TAF FDC once daily for up to 96 weeks.

#### **5.4.** Prior and Concomitant Medications

- The use of medications for the treatment of HIV, other than study drug, is prohibited.
- Medications listed in the following table and use of herbal/natural supplements are excluded
  or should be used with caution while subjects are participating in the study. Subjects will
  refrain from consumption of grapefruit juice and Seville orange juice throughout
  participation in the study.

Table 5-1. Prior and Concomitant Medications

Drug Class	Agents Disallowed*	Use Discouraged and To Be Used With Caution
Acid Reducing Agents Antacids Buffered medications		Concentration of study drug may decrease with antacids. Subjects may not take antacids (eg, Tums or Rolaids); the ulcer medication sucralfate (Carafate); or vitamin or mineral supplements that contain calcium, iron or zinc for a minimum of 6 hours before and 2 hours after any dose of study drug.
Antiarrhythmic Agent	Dofetilide	
Anticonvulsants	Phenobarbital, Phenytoin, Carbamazepine, Oxcarbazepine	
Antimycobacterials	Rifampin, Rifapentine	
Antiretrovirals	Any antiretroviral drug that is not part of the study regimen	
GI Motility Agents	Cisapride	
Herbal/Natural Supplements	St. John's Wort, Echinacea	
Oral Hypoglycemic Agent		Metformin: close monitoring is recommended.  A dose adjustment of Metformin may be necessary. Limit total daily doses of Metformin to 1000mg when initiating study medication or if initiating metformin while on study drug.

\* Administration of any of the above medications must be discontinued at least 30 days prior to the Day 1 visit and for the duration of the study.

Should subjects have a need to initiate treatment with any excluded concomitant medication, the Gilead Medical Monitor must be consulted prior to initiation of the new medication. In instances where an excluded medication is initiated prior to discussion with the Sponsor, the Investigator must notify Gilead as soon as he/she is aware of the use of the excluded medication.

## 5.5. Accountability for IMP

Subjects will be instructed to bring all study medication in the original container at each clinic visit for drug accountability. The Investigator will be responsible for maintaining accurate records for all study drug bottles dispensed and tablets returned. The inventory and dispensing logs must be available for inspection by the study monitor. Study medication supplies, including partially used or empty bottles, must be accounted for by the study monitor prior to destruction or return.

The investigator is responsible for ensuring adequate accountability of all used and unused IMP. This includes acknowledgement of receipt of each shipment of IMP (quantity and condition). All used and unused IMP dispensed to subjects must be returned to the site.

Study Drug accountability records will be provided to each study site to:

- Record the date received and quantity of IMP kits
- Record the date, subject number, subject initials, the IMP kit number dispensed
- Record the date, quantity of used and unused IMP returned, along with the initials of the person recording the information

# 5.5.1. IMP Return or Disposal

Study drug return and disposal will be performed as outlined in Section 9.1.7.

# 6. STUDY PROCEDURES

The study procedures to be conducted for each subject enrolled in the study are presented in tabular form in Appendix 2 and described in the text that follows.

The investigator must document any deviation from protocol procedures and notify the sponsor or contract research organization (CRO).

# 6.1. Subject Enrollment and Treatment Assignment

It is the responsibility of the Investigator to ensure that subjects are eligible for study prior to enrollment. Please refer to Section 6.2.2 for details about randomization and treatment assignment.

#### 6.2. Pretreatment Assessments

### **6.2.1.** Screening Visit

Subjects will be screened within 30 days before Day 1 to determine eligibility for participation in the study. The following will be performed and documented at screening:

- Obtain written informed consent(s)
- Obtain medical history including history of HIV-1 disease-related events, and prior medications within 30 days of the screening visit
- If available, obtain documentation of historical genotype(s) (not required for entry to study)
- Complete physical examination (urogenital/anorectal exams will be performed at the discretion of the Investigator)
- 12-lead ECG performed supine
- Height
- Vital signs measurement (blood pressure, pulse, respiration rate, and temperature), including weight
- Obtain blood and urine samples as described in Sections 6.10.1 and 6.10.2
- Review concomitant medications
- Record any SAEs and all AEs related to protocol mandated procedures occurring after signing of the consent form

Subjects meeting all of the inclusion criteria, and none of the exclusion criteria, will return to the clinic within 30 days after screening for the Day 1 Visit into the study. Subjects must continue to take their prior treatment regimen up until their scheduled Day 1 visit.

From the time of obtaining informed consent through the first administration of study drug, record all SAEs, as well as any AEs related to protocol-mandated procedures on the adverse events eCRF. All other untoward medical occurrences observed during the screening period, including exacerbation or changes in medical history are to be captured on the medical history eCRF. See Section 7 Adverse Events and Toxicity Management for additional details.

# 6.2.2. Day 1 Assessments

The following evaluations are to be completed at the Day 1 Visit. The Investigator must have confirmed eligibility before proceeding with the Day 1 visit. The subject must complete all study procedures before being administered the study drug:

- Short Form 36 Health Survey (SF-36), HIV Symptoms Distress Module, Work Productivity and Activity Impairment Questionnaire (WPAI) and Pittsburgh Sleep Quality Index (PSQI) to be completed by the subject. Subject is to read questionnaire by himself/herself and write/mark answers directly onto questionnaires.
- Review of AEs and changes in concomitant medications
- Complete physical examination (urogenital/anorectal exams will be performed at the discretion of the Investigator)
- Vital signs measurement (blood pressure, pulse, respiration rate, and temperature), including weight
- Obtain blood and urine samples as described in Sections 6.10.1 and 6.10.2.
- Dispense study drug
- Observed first dose administration of the assigned study drugs as described in Section 5.3
- Subjects should be instructed to take study drugs without regard to food. The subject should be counseled regarding the importance of adherence and taking their study medications at approximately the same time each day as directed by the Investigator.

## 6.3. Randomization

Once eligibility has been confirmed, prior to or during the Day 1 visit, the Investigator or designee will randomize the subject using IWRS. Once a subject number has been assigned to a subject, it will not be reassigned to any other subject. The subject number assignment and randomization may be performed up to 3 days prior to the in-clinic Day 1 visit provided that all screening procedures have been completed, and subject eligibility has been confirmed.

# 6.4. Treatment Assessments (Week 4 - 48)

The following evaluations are to be completed at Weeks 4, 8, 12, 24, 36, and 48 unless otherwise specified.

Study visits are to be completed within  $\pm$  2 days of the protocol specified visit date (based on the Day 1 visit) through Week 12, and completed within  $\pm$  6 days of the protocol specified visit date through Week 36, unless otherwise specified. The visit window at Week 48 will be  $\pm$  6 weeks of the protocol specified visit date, and this clinical visit window coincides with the Week 48 statistical analysis window for HIV-1 RNA.

Regularly scheduled evaluations will be made on all subjects whether or not they continue to receive study drug.

- SF-36, HIV Symptoms Distress Module, WPAI and PSQI to be completed by the subject at Weeks 4, 12 and 48. Subject is to read questionnaire by himself/herself and write/mark answers directly onto questionnaires
- Review of AEs and changes in concomitant medications
- Complete physical examination (Weeks 24 and 48) (urogenital/anorectal exams will be performed at the discretion of the Investigator) or symptom-directed physical examination, as needed
- Vital signs measurement (blood pressure, pulse, respiration rate, and temperature), including weight
- Obtain blood and urine samples as described in Sections 6.10.1 and 6.10.2
- Document study drug dispensation and accountability for all study drugs dispensed.
- Subjects who meet the criteria for virologic failure will be managed according to the Management of Virologic Rebound Section 6.11.1 and 6.11.2

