#### 8.5.1.1. US FDA-defined Snapshot Algorithm

The analysis window at Week 48 is defined as from Study Day 295 to Study Day 378, inclusive. All HIV-1 RNA data collected on-treatment (ie, including data collected up to 1 day after the last dose date of study drug) will be used in the snapshot algorithm. Virologic outcome will be defined as the following categories:

- **HIV-1 RNA < 50 copies/mL**: this includes subjects who have the last available on-treatment HIV-1 RNA < 50 copies/mL in the Week 48 analysis window
- HIV-1 RNA  $\geq$  50 copies/mL: this includes subjects
  - a) Who have the last available on-treatment HIV-1 RNA ≥ 50 copies/mL in the Week 48 analysis window, or

- b) Who do not have on-treatment HIV-1 RNA data in the Week 48 analysis window and
  - 1. Who discontinue study drug prior to or in the Week 48 analysis window due to lack of efficacy, or
  - 2. Who discontinue study drug prior to or in the Week 48 analysis window due to reason other than lack of efficacy and have the last available on-treatment HIV-1 RNA ≥ 50 copies/mL
- No Virologic Data in the Week 48 Analysis Window: this includes subjects who do not have on-treatment HIV-1 RNA data in the Week 48 analysis window because of the following:
  - a) Discontinuation of study drug prior to or in the Week 48 analysis window due to reasons other than lack of efficacy and the last available on-treatment HIV-1 RNA
     < 50 copies/mL, or

  - b) Missing data during the window but on study drug

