# PPD

[figure not shown]
CD4+ Cell Count and Percentage	X	X	X	X	X	X	X	X	X	X	X	X	X	X	X	X	X	X	X	X
HCV Serology s	X							X	X 					X				X		
HBV blood panelt	X u							Xu	X u					Xu				Xu		
Plasma HBV DNA v		X	X	X	X	X	X	X	X	X	X	X	X	X	X	X	X	X		X
Randomizationw		X																		
Study Drug Dispensation		Xx	X	X	X	X	X	X	X	Xy	X	X	X	X	X	X	X			
Study Drug Accountability			X	X	X	X	X	X	X	X	X	X	X	X	X	X	X	X		X
HIV-1 Genotype/ Phenotype c																				Xc
PPD																				

- a. Evaluations to be completed within 30 days prior to Day 1.
- b. Study visits are to be completed within ± 2 days of the protocol specified visit date (based on the Day 1) through Week 12 and within ± 6 days through to Week 36, unless otherwise specified. The visit window for Week 48 will be ± 6 weeks of the protocol specified visit date.
- c. HIV-1 genotype and phenotype testing for subjects with confirmed virologic failure and HIV-1 RNA >200 copies/mL. Following virologic rebound, subjects will be asked to return to the clinic (2-3 weeks later) prior to the next scheduled visit or at the next scheduled study visit for a HIV-1 RNA and HIV-1 resistance analysis (reverse transcriptase, protease, and integrase genotype and phenotype) blood draw. Based on the results of this testing, subjects should be managed according to the Virologic Rebound Schema (Section 6.11).
- d. After Week 48, all subjects will continue to take their blinded study drug and attend visits every 12 weeks (± 6 days of the protocol specified visit date) until the End of Blinded Treatment Visit.
- e. Once the last subject completes the Week 48 visit and Gilead completes the Week 48 analysis, all subjects will return to the clinic (preferably within 30 days) for an End of Blinded Treatment Visit. At the End of Blinded Treatment Visit, if safety and efficacy of B/F/TAF is demonstrated following review of unblinded data, subjects in a country where B/F/TAF FDC is not available, will be given the option to receive B/F/TAF FDC in an OL extension phase for up to 96 weeks, or until the product becomes accessible to subjects through an access program, or until Gilead elects to discontinue the study in that country, whichever occurs first. Treatment assignments will be provided to the investigators within 30 days of the last subject completing the End of Blinded Treatment Visit.

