# Study Day 1 for the all B/F/TAF analysis is defined as

- For subjects who actually received B/F/TAF in the randomized phase of this study (ie, B/F/TAF group), **Study Day 1** for the all B/F/TAF analysis is defined as the day when the first dose of B/F/TAF in the randomized phase was taken, as recorded on the Study Drug Administration eCRF form.
- For subjects who actually received DTG + F/TAF in the randomized phase of this study and then receive at least 1 dose of B/F/TAF in the extension phase (ie, DTG + F/TAF to B/F/TAF group), **Study Day 1** for the all B/F/TAF analysis is defined as the day when the first dose of B/F/TAF in the extension phase was taken (ie, OL B/F/TAF), as recorded on the Study Drug Administration eCRF form.

Last Dose Date for the All B/F/TAF Analysis is the latest of B/F/TAF (including both randomized phase and open label phase) end dates recorded on the Study Drug Administration eCRF form.

If the last dose date for the all B/F/TAF analysis is missing (eg, only year of last dose date is known or completely missing due to lost to follow-up), the latest of the B/F/TAF (including both randomized phase and open label phase) start dates and end dates, the latest clinical and laboratory visit dates, excluding the 30-day follow-up visit date, will be used to impute the last dose date.

**Study Days** are calculated relative to Study Day 1 for the randomized phase analysis. For events that occurred on or after the Study Day 1 date, study days are calculated as (visit date minus Study Day 1 plus 1). For events that occurred prior to Study Day 1 for either analysis, study days are calculated as (visit date minus Study Day 1).

**Last Study Date** is the latest of the study drug (including DTG + F/TAF, and B/F/TAF in both randomized phase and open label phase) start dates and end dates, the clinic visit dates, and the laboratory visit dates, including the 30-day follow-up visit date.

**Baseline Value** is defined as the last nonmissing value obtained on or prior to Study Day 1 for the randomized phase analysis or the all B/F/TAF analysis, as appropriate. Subjects who actually received DTG + F/TAF in the randomized phase and received at least 1 dose of B/F/TAF in extension phase will have a baseline for Randomized Phase Analysis and a new baseline value for the all B/F/TAF analysis.

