# 3.8.2. Analysis Windows

Subject visits might not occur on protocol specified days. Therefore, for the purpose of analysis, observations will be assigned to two different analysis windows based on the following tables: the analysis windows for the randomized phase analysis are derived relative to the Study Day 1 for the randomized phase analysis, while the analysis windows for the all B/F/TAF analysis are derived relative to the Study Day 1 for the all B/F/TAF analysis.

The analysis windows for HIV-1 RNA, CD4+ cell count, CD4 %, hematology, chemistry, urinalysis, urine pregnancy laboratory tests, eGFRCG, vital signs, and weight are presented in Table 2 and Table 3 for randomized phase analysis and all B/F/TAF analysis separately.

Table 2. Analysis Windows for HIV-1 RNA, CD4+ cell count, CD4 %, HBV DNA, Hematology, Chemistry, Urinalysis, and Urine Pregnancy Laboratory Tests, eGFRCG, Vital Signs, and Weight for Randomized Phase Analysis

Visit ID	Nominal Day	Lower Limit	Upper Limit
Baseline			1
Week 4	28	2	42
Week 8	56	43	70
Week 12	84	71	126
Week 24	168	127	210
Week 36	252	211	294
Week 48	336	295	378
Week 60	420	379	462
Week 72	504	463	546
Week 84	588	547	630
Week K	K*7	(K-6)*7+1	(K+6)*7

Note: Week K is every 12 weeks after previous visit.

Table 3. Analysis Windows for HIV-1 RNA, CD4+ cell count, CD4 %, HBV DNA, Hematology, Chemistry, Urinalysis, and Urine Pregnancy Laboratory Tests, eGFRCG, Vital Signs, and Weight for All B/F/TAF Analysis

	B/F/TAF Group			DTG+F/TAF to 1		
Visit ID	Nominal Day	Lower Limit	Upper Limit	Nominal Day	Lower Limit	Upper Limit
Baseline			1			1
Week 4	28	2	42	NA	NA	NA
Week 8	56	43	70	NA	NA	NA
Week 12	84	71	126	84	2	126
Week 24	168	127	210	168	127	210
Week 36	252	211	294	252	211	294
Week 48	336	295	378	336	295	378
Week 60	420	379	462	420	379	462
Week 72	504	463	546	504	463	546
Week 84	588	547	630	588	547	630
Week 96	672	631	714	672	631	714
Week k	K*7	(K-6)*7+1	(K+6)*7	K*7	(K-6)*7+1	(K+6)*7

NA = Not applicable

Note: For the B/F/TAF group, Study Day 1 is the first dose date of the B/F/TAF received in the randomized phase; For the DTG + F/TAF to B/F/TAF group, Study Day 1 is the first dose date of the B/F/TAF received in the extension phase.

Note: Week K is every 12 weeks after previous visit.

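### The ±6-week Week 48 visit window spans 85 days and the HIV-1 RNA analysis window 84, so one permitted visit day falls outside the primary endpoint window

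*Protocol*

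**What the plan says.** Protocol Section 6.4 gives the Week 48 visit a window of ±6 weeks, much wider than the windows for earlier visits, and adds that "this clinical visit window coincides with the Week 48 statistical analysis window for HIV-1 RNA". Footnote b of the procedures table (Protocol Appendix 2) repeats the width without the remark about coincidence: "The visit window for Week 48 will be ± 6 weeks of the protocol specified visit date". SAP Appendix 1 carries the same footnote.

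The analysis window is given in days. Protocol Section 8.5.1.1 states: "The analysis window at Week 48 is defined as from Study Day 295 to Study Day 378, inclusive". SAP Section 6.1.1.2 agrees, and the row in SAP Table 2 (Section 3.8.2) reads "Week 48 336 295 378": nominal day, lower limit, upper limit.

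SAP Section 3.8.1 takes the first dose of blinded drug as Study Day 1. For later dates, "study days are calculated as (visit date minus Study Day 1 plus 1". Protocol Section 6.2.2 has the first dose observed at the Day 1 visit, so the Day 1 visit and Study Day 1 are the same date.

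**The concern.** Only Week 48 has so wide a visit window and a statement that it matches the analysis window. The evident purpose is that every Week 48 sample taken on time should count. The snapshot algorithm applies fixed, inclusive day limits, so a one-day mismatch decides whether an edge-day sample is used.

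A subject still on drug, with no on-treatment result in the window, goes to the category for no virologic data (Protocol 8.5.1.1; SAP 6.1.1.2). Three results follow:

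- In the primary endpoint the subject stays in the denominator and is not a failure, even if the edge-day value was ≥ 50 copies/mL.
- In the < 50 copies/mL endpoint a suppressed edge-day value becomes a non-response.
- The subject is excluded from the Week 48 per-protocol set (Protocol 8.2.1.2.2; SAP Table 1).

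**Working it through.** **1. Reproduce the analysis window.** The rule in SAP Table 2 for week K is (K − 6) × 7 + 1 to (K + 6) × 7. With K = 48, the lower limit is 42 × 7 + 1 = 295 and the upper limit is 54 × 7 = 378. This matches the stated window. Its length is 378 − 295 + 1 = 84 days.

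**2. Count the visit window.** ±6 weeks is ±42 days. With both edges included, the length is 42 + 1 + 42 = 85 days.

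**3. Place it on the study-day scale.** The documents support two anchors for Week 48.

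| Anchor | Visit window | Day not covered | SAP Table 2 assigns it to |
|---|---|---|---|
| SAP nominal Day 336 | 294–378 | 294 | Week 36 (211–294) |
| Day 1 + 336 days = Study Day 337 | 295–379 | 379 | Week 60 (379–462) |

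An 85-day interval cannot coincide with an 84-day one, whichever anchor is used.

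**4. Check whether another planned visit fills the window.** Weeks 36 and 60 have windows of ±6 days (Protocol 6.4, 6.5.1). Across both anchors, Week 36 falls in Days 246–259 and Week 60 in Days 414–427. Neither reaches Days 295–378, so a lone edge-day sample leaves the window empty unless there is an unscheduled sample.

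**5. Check the retest rule.** Section 6.11.1 asks for a confirmatory sample 2 to 3 weeks after a value ≥ 50 copies/mL.

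- After Day 294 that is Days 308–315, inside the analysis window, so the retest would be scored.
- After Day 379 it is Days 393–400, outside the window.
- A retest taken on Day 379 implies a first sample on about Days 358–365. That value, ≥ 50 copies/mL, is in the window and is scored as a failure. A suppressed retest on Day 379 would not replace it.

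**6. Size.** One day in 85 is 1.2%. One subject is 1/260 = 0.38 percentage points of a planned arm. The number of edge-day subjects is not in the documents, so it is shown as a range of assumptions. The planning failure rate of 2% (Protocol 8.8) is applied to each.

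| Assumption on visit timing | Edge-day subjects | Expected with RNA ≥ 50 |
|---|---|---|
| Most visits close to Week 48 | 0–2 | at most 2 × 0.02 = 0.04 |
| All 565 treated subjects spread evenly over 85 days | 565/85 = 6.6 | 6.6 × 0.02 = 0.13 |
| 5–10% of 565 in the last 7 days, spread evenly | 28/7 to 57/7, about 4–8 | 0.08–0.16 |

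The first row is the most plausible. The other two show that the answer stays small under unfavourable timing.

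**The case against.** **The edge day may not be permitted.** The sentence that gives ±6 weeks also ties the visit window to the analysis window, which the same protocol fixes at Days 295–378. Read together, Day 294 or 379 could be taken as out of range. But sites are given ±6 weeks in two places, footnote b does not mention the analysis window, and Section 6.4 gives no day numbers.

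**The anchor is not fixed.** The phrase about counting from the Day 1 visit, "of the protocol specified visit date (based on the Day 1 visit) through Week 12", belongs to the clause on early visits. The only nominal day stated for Week 48 is 336, where the late edge matches exactly and only Day 294 is uncovered. This stands: it cannot be said that the late edge is the one lost. It moves the gap but does not close it.

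**The scoring is conditional.** This also stands. A subject with another on-treatment sample in Days 295–378 is scored on that sample. A Day 294 value ≥ 50 copies/mL would normally be retested in the window. A subject who stops drug before or in the window for lack of efficacy, or with a last on-treatment value ≥ 50 copies/mL, and has no in-window sample is scored as a failure.

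**A stronger reading is tempting.** A reader might infer that a handful of edge-day subjects could decide the trial. With 565 subjects split almost equally (an assumption), the unconditional exact test at the 4% margin passes at 8 versus 6 failures (one-sided p about 0.015) and fails at 9 versus 6 (about 0.028). Three further failures on B/F/TAF would therefore reverse a 6 versus 6 result. But an edge-day subject alters the failure count only if HIV-1 RNA is ≥ 50 copies/mL. Even with eight such subjects at 2% each, the chance of three or more failures is about 56 × 0.02³ × 0.98⁵ = 0.04%, before requiring all of them to be on B/F/TAF. Nor do the documents support the idea that visits bunch on the last permitted day.

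**Conclusion.** The statement in Protocol Section 6.4 is wrong by one day. The day count is exact and does not depend on the anchor; only the identity of the lost day does. A visit made within the stated ±6 weeks can therefore supply no usable primary-endpoint result, provided the subject is still on drug and has no other on-treatment sample in Days 295–378.

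The practical effect is very small. Assuming most visits fall near Week 48, 0 to 2 subjects are affected, with at most 0.04 expected missed failures at the planning rate. In the < 50 copies/mL endpoint, two subjects in the same arm would move the difference by 2/260 = 0.77 percentage points, against a 10% margin. The planned sample size and power are not affected. The mismatch is unlikely to change the non-inferiority conclusion and is a minor correction.

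**What to change.** State the Week 48 visit and retest window as Study Day 295 to 378, with Day 1 as the date of first dose, in Protocol Sections 6.4 and 6.11.2 and in Appendix 2 footnote b. Carry the same wording into the copied footnote in SAP Appendix 1. The analysis window itself should stay as it is.

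The cost is one permitted visit day and a minor protocol amendment, which needs ethics approval before it takes effect (Protocol 9.1.2, 9.2.1).

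SAP Section 2.2.1 reports that the Week 48 analysis has been conducted, so an amendment cannot recover visits already made. The useful step now is to list in the study report, by arm and with the HIV-1 RNA value, any subject whose only Week 48 sample fell on Day 294 or Day 379. If there are none, the point is closed.
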